9.3. Other resources available

- *This study requires a small number of healthy participants. Given the registry maintained by the CTSC along with the number of healthy people who frequent the UNM campus and may see our flier, we believe it will be feasible to recruit our sample.*
- *Our study team will devote ample time to the all phases of this research project. Time necessary may fluctuate depending on how many participants are interested at a particular time. Our team comprises of several individuals with the training and expertise necessary to devote the time needed until the project is completed.*
- *Laboratory space and equipment: [name], Noninvasive Neurostimulation Laboratory at UNM (476 nsf), is housed at the University of New Mexico Clinical and Translational Science Center (CTSC) on the second floor of the building. On this floor, a main reception area and front desk check-in for study appointments. The lab contains all equipment necessary to conduct noninvasive transcranial magnetic stimulation (TMS) studies. Both a Magstim 200² (plus the Bistim² unit) (Magstim Co., Whitland, Dyfed, UK) and a Magstim Rapid² (Magstim Co., Whitland, Dyfed, UK) are used in the laboratory. The coil inventory includes a Magstim double 70mm coil, Magstim custom double 35mm coils, and Magstim double 70mm cooled coil system and a Magstim double 70mm sham coil system (1st generation), (Magstim Co., Whitland, Dyfed, UK). For this project, a set of real vs. sham Magstim (2nd generation) air-cooled coils are requested to match the same set of coils in use at all other sites. The TMS units are connected to a commercial electromyography machine (Nicolet Viking) through a data acquisition device (Micro 1401, Cambridge Electronic Devices, Cambridge, UK). The data are collected and analyzed through Signal software (Cambridge Electronic Devices, Cambridge, UK). The lab is also equipped with custom hardware, including a flexible overhead coil holders and optional chin-rest and neck brace for stabilizing the subject's head during experiments and chair with arm and leg rests.*
- *A NeuroConn MR transcranial electrical stimulator belonging to the Clinical Core will be used. This is a CE-certified medical device for conducting non-invasive transcranial direct current stimulation (tDCS), alternating (tACS) or random noise (tRNS) current stimulation on subjects. Transcranial stimulation using weak electric currents over a period of several minutes is demonstrated to modify neuronal excitability and circuit function and can serve to promote brain recovery and repair.*

PROTOCOL TITLE: *Metaplasticity in the human motor cortex: validation of an experimental design and comparison of motor outcome measure sensitivity to change*

- *Although risk for seizure is minimal, in the event this occurs the PI ([name]) will be on hand to administer immediate first aid and the hospital code team would be activated.*
- *All members of our small study team are involved in the development of this protocol. Upon approval, we will meet regularly to ensure that our research protocol is being appropriately implemented. Furthermore, there will be at least two members of the research team available for participant visits, ensuring accountability and safety procedures are being met.*
- *The signed CTSC resources attachment will be uploaded on the CTSC Submission page in Click.*

10. Prior Approvals

10.1. N/A

10.2. Attached to submission

10.3. N/A

10.4. N/A

11. Multi-Site Research

11.1. N/A

11.2. N/A

11.3. N/A

12. Study Procedures

12.1. *Visit 1: After informed consent, subjects will be seated in a comfortable chair. Surface EMG leads will be applied to clean and prepped skin over the right hand over the first dorsal interosseous muscle (FDI). The motor hotspot for FDI will be identified with TMS on the contralateral hemisphere. Resting motor threshold and active motor threshold will be determined.*

- **M1** (pre-tDCS measurement): neurophysiological outcome assessment (MEP, CSP) and behavioral outcome (reaction time task)
- **Priming Intervention** 10 min tDCS (cathodal, anodal or sham)
- **M2** (pre-tDCS measurement): neurophysiological outcome assessment (MEP, CSP) and behavioral outcome (reaction time task)
- **Inhibitory Intervention** 15 min rTMS over the dominant primary motor cortex at 1Hz
- **M3** (post-rTMS measurement): neurophysiological outcome assessment (MEP, CSP) and behavioral outcome (reaction time task)
- **M4** (10 minutes post-rTMS measurement): neurophysiological outcome assessment (MEP, CSP) and behavioral outcome (reaction time task)

PROTOCOL TITLE: *Metaplasticity in the human motor cortex: validation of an experimental design and comparison of motor outcome measure sensitivity to change*

Visit 2:

- **M1** (pre-tDCS measurement): neurophysiological outcome assessment (MEP, CSP) and behavioral outcome (reaction time task)
- **Priming Intervention** 10 min tDCS (cathodal, anodal or sham)
- **M2** (pre-tDCS measurement): neurophysiological outcome assessment (MEP, CSP) and behavioral outcome (reaction time task)
- **Inhibitory Intervention** 15 min rTMS over the dominant primary motor cortex at 1Hz
- **M3** (post-rTMS measurement): neurophysiological outcome assessment (MEP, CSP) and behavioral outcome (reaction time task)
- **M4** (10 minutes post-rTMS measurement): neurophysiological outcome assessment (MEP, CSP) and behavioral outcome (reaction time task)

Visit 3:

- **M1** (pre-tDCS measurement): neurophysiological outcome assessment (MEP, CSP) and behavioral outcome (reaction time task)
- **Priming Intervention** 10 min priming tDCS (cathodal, anodal or sham)
- **M2** (pre-tDCS measurement): neurophysiological outcome assessment (MEP, CSP) and behavioral outcome (reaction time task)
- **Inhibitory Intervention** 15 min rTMS over the dominant primary motor cortex at 1Hz
- **M3** (post-rTMS measurement): neurophysiological outcome assessment (MEP, CSP) and behavioral outcome (reaction time task)
- **M4** (10 minutes post-rTMS measurement): neurophysiological outcome assessment (MEP, CSP) and behavioral outcome (reaction time task)

13. Data Analysis

13.1. Aim 1: To compare pre- and post- measures of cortical excitability after inhibitory and excitatory priming of the motor cortex. Hypothesis 1: We expect priming tDCS to affect the response to rTMS, namely we expect “inhibitory” cathodal tDCS to cause a reversal of the normal inhibitory effect of 1Hz rTMS. Hypothesis 2: We expect “excitatory” anodal tDCS to have no effect on the normal inhibitory effect of 1Hz rTMS. Hypothesis 3: We expect sham tDCS to have no effect on the normal inhibitory effect of 1Hz rTMS. We will use a MANOVA model (anodal, cathodal, and sham) and a specified number of

PROTOCOL TITLE: *Metaplasticity in the human motor cortex: validation of an experimental design and comparison of motor outcome measure sensitivity to change*

variables (time points—M1-M4). MANOVA assumes normality of the residuals and equality of variance across groups. In the case of violation of these assumptions, we will explore data transformations, including logarithmic, power, and inverse-normal transformations, to identify an analytic scale under which modeling assumptions are met. Should transformations not be adequate, we will employ non-parametric methods instead.

Exploratory Aim 2: To evaluate the sensitivity of motor outcome measures to changes in cortical plasticity. Hypothesis 1: We expect different measures of motor cortex excitability to be more sensitive than others at detecting changes in cortical excitability. We will be comparing in an exploratory but systematic fashion various measures of motor cortex excitability (e.g. peak-to-peak amplitude change in motor evoked potential (MEP) and the integrated area of the MEP (root mean square)) with the cortical silent period (CSP) and behavioral measures (reaction time). We will perform both a linear regression as well as a Principal Components Analysis (PCA) to identify which cortical excitability factors are most sensitive to change due to noninvasive neurostimulation.

13.2. *Power analysis:* Sixteen subjects will be enrolled for this study according to the MANOVA model (anodal, cathodal, and sham) and a specified number of variables (time points—M1-M4) at the significance level of $\alpha=0.05$ and 80% power to correspond to the very large effect size. We have based the calculation on the very large effect size as seen in Quartarone et al., 2005. The desired sample size was found to be 16 patients per treatment arm. We will fulfill this sample size requirement through a crossover trial as all 16 subjects will participate in each treatment arm. We would request a recruitment ceiling of 20 subjects to account for subject dropout and if a subject were to meet exclusion criteria after signing the consent.

14. Provisions to Monitor the Data to Ensure the Safety of Subjects

14.1. The PIs will consist of the medical monitoring team for this study due to its minimal risk status.

14.2. We will collect data on the safety of rTMS including expected side effects: headache (expected 17% with transient headache that responds to simple analgesic) and nonspecific feelings of discomfort. We will collect data on rare but serious adverse events such as seizures (reported at 1.4%).

14.3. The safety data will be reviewed on an ongoing basis during enrollment and conduct of the study.

14.4. We plan to follow the most recent safety recommendations from expert consensus panels on rTMS.

14.5. We have no planned formal analysis of the safety data.

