ICH-GCP E6 can be accessed by copying and pasting this URL into your browser: <http://www.fda.gov/downloads/Drugs/Guidances/ucm073122.pdf>

Table of Contents

1. Objectives	4
2. Background	4
3. Study Design	5
4. Inclusion and Exclusion Criteria	5
5. Number of Subjects	6
6. Study Timelines	6
7. Study Endpoints	6
8. Research Setting	7
9. Resources Available	7
10. Prior Approvals	7
11. Multi-Site Research	8
12. Study Procedures	8
13. Data Analysis	8
14. Provisions to Monitor the Data to Ensure the Safety of Subjects	9
15. Withdrawal of Subjects	9
16. Data Management/Confidentiality	9
17. Data and Specimen Banking	11
18. Risks to Subjects	11
19. Potential Benefits to Subjects	11
20. Recruitment Methods	12
21. Provisions to Protect the Privacy Interests of Subjects	12
22. Economic Burden to Subjects	12
23. Compensation	13
24. Compensation for Research-Related Injury	13
25. Consent Process	14
26. Documentation of Consent	16
27. Study Test Results/Incidental Findings	17
28. Sharing Study Progress or Results with Subjects	18
29. Inclusion of Vulnerable Populations	18
30. Community-Based Participatory Research	19
31. Research Involving American Indian/Native Populations	19
32. Transnational Research	19
33. Drugs or Devices	19
Checklist Section	20

1. Objectives

1.1. *The overall objective is to validate the methodology of a metaplasticity experimental design by assessing change in motor excitability after administration of priming transcranial direct current stimulation (tDCS) followed by repetitive transcranial magnetic stimulation (rTMS) in healthy human participants. Our primary objective is to compare pre- and post-measures of cortical excitability before priming tDCS (anodal, cathodal or sham) [M1], directly after priming tDCS [M2], directly after inhibitory rTMS [M3], and 10 minutes after inhibitory rTMS [M4]. Our secondary objective is to evaluate the sensitivity of motor excitability outcome measures response to the noninvasive neurostimulation (e.g. rTMS and tDCS). Our future direction is to apply this validated protocol in patient populations to better understand how disease states affect metaplasticity.*

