1.2. *Aim 1: To compare pre- and post- measures of cortical excitability after inhibitory and excitatory priming of the motor cortex. Hypothesis 1: We expect priming tDCS to affect the response to rTMS, namely we expect “inhibitory” cathodal tDCS to cause a reversal of the normal inhibitory effect of 1Hz rTMS. Hypothesis 2: We expect “excitatory” anodal tDCS to have no effect on the normal inhibitory effect of 1Hz rTMS. Hypothesis 3: We expect sham tDCS to have no effect on the normal inhibitory effect of 1Hz rTMS.*

Exploratory Aim 2: To evaluate the sensitivity of motor outcome measures to changes in cortical plasticity. Hypothesis 1: We expect different measures of motor cortex excitability to be more sensitive than others at detecting changes in cortical excitability. We will be comparing in an exploratory but systematic fashion various measures of motor cortex excitability (e.g. peak-to-peak amplitude change in motor evoked potential (MEP), the integrated area of the MEP (root mean square), the cortical silent period (CSP)), and behavioral measures (reaction time).

2. Background

2.1. *rTMS and tDCS are relatively new modalities that have shown promise in the evaluation and treatment in a variety of neurologic and psychiatric disorders as well as understanding normal brain processes in the healthy human brain. One specific area of interest has been the concept of metaplasticity in the motor cortex in healthy brains and how this is modified in the disease state. Metaplasticity refers to changes in synaptic efficacy such as long-term potentiation (LTP) and long-term depression (LTD), which can be influenced by prior neuronal activity. In humans, we can study these LTP-like and LTD-like changes using non-invasive neurostimulation (e.g. tDCS and rTMS).*

2.2. *Previous studies (Siebner et al. 2004) have shown that preconditioning with anodal (“excitatory”) tDCS followed by inhibitory rTMS led to a period in which corticospinal excitability was reduced below baseline. Conversely, preconditioning with cathodal tDCS followed by 1Hz rTMS caused a resulting*

PROTOCOL TITLE: *Metaplasticity in the human motor cortex: validation of an experimental design and comparison of motor outcome measure sensitivity to change*

period of corticospinal excitability that was increased above baseline. This will be a proof of principle trial to validate the methodology of this protocol.

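### The one Aim 1 test, an omnibus MANOVA, does not isolate the cathodal reversal, and Hypotheses 2 and 3 as worded are not matched to a test that could support them

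*Combined protocol and SAP*

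**What the plan says.** Section 13.1 repeats the three hypotheses of 1.2. Cathodal priming is expected to "cause a reversal of the normal inhibitory effect of 1Hz rTMS". Hypothesis 2 expects "anodal tDCS to have no effect on the normal inhibitory effect of 1Hz rTMS". Hypothesis 3 reads "We expect sham tDCS to have no effect on the normal inhibitory effect of 1Hz rTMS".

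The analysis that follows begins "We will use a MANOVA model (anodal, cathodal, and sham", with the time points M1 to M4 as the variables. After that come only assumption checks, transformations and an unnamed non-parametric fallback. Section 13.2 repeats the same MANOVA for the sample size, at alpha 0.05 and 80% power, for an effect described only as very large.

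Other sections bear on how to read this:

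- The aim itself is "To compare pre- and post- measures of cortical excitability after inhibitory and excitatory priming of the motor cortex".
- Section 1.1 places the measures before tDCS (M1), then "directly after priming tDCS [M2], directly after inhibitory rTMS [M3", with M4 ten minutes later.
- Section 7.1 makes change in MEP amplitude the primary endpoint. It defines the intervention as tDCS plus rTMS, refers to M1 to M3, and adds M4.
- Section 2.2 says that in earlier work anodal priming followed by inhibitory rTMS gave a period in which "corticospinal excitability was reduced below baseline", and that cathodal priming gave a "period of corticospinal excitability that was increased above baseline".

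**The concern.** The study is meant to validate a method, so a reader should be able to say in advance which result would support or contradict each hypothesis. Section 13.1 does not allow that.

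An omnibus test can reject for reasons unrelated to the reversal: a chance imbalance at M1, a direct effect of tDCS at M2, or an anodal-sham difference. The no-effect wording of Hypotheses 2 and 3 invites support from a non-significant result, which in a trial of this size is compatible with a moderate real difference.

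The word reversal also depends on the reference. If cathodal tDCS lowers M2 and excitability then only returns to its M1 level, the change from M2 is a rise while the change from M1 is nil.

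**Working it through.** **The plan's own figure.** The sample size of 16 cannot be reproduced, because 13.2 gives no number for the effect. Solving backwards for 80% power at 16 gives a standardised difference of 1.02 for a two-sample t-test (16 per arm), 0.75 SD of the paired difference for a paired t-test, or f² = 0.17 for a three-group, four-variable MANOVA. These do not show that 16 is wrong. They show that it does not reveal which contrast, if any, was powered.

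**Step 1: what the omnibus test covers.** Three conditions and four variables give (3 − 1) × 4 = 8 between-condition comparisons. If the test is of condition by time, there are (3 − 1) × (4 − 1) = 6. The cathodal minus sham difference in change is one direction among these. Rejecting the joint null does not say that this direction, or its sign, is responsible.

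**Step 2: two readings of Hypotheses 2 and 3.**

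| Reading | Test needed | What the plan offers |
|---|---|---|
| Comparative: priming does not alter the rTMS response | A comparator without that priming, and a CI or equivalence margin | Anodal can be compared with sham. Sham has no comparator, since every visit in 12.1 gives cathodal, anodal or sham tDCS before rTMS. No margin is given. |
| Within-visit: inhibition still occurs after this priming | A test of the fall in MEP amplitude within that visit | A difference test is the right tool, but none is named. |

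The pre/post wording of the aim fits the second reading. The literal wording of the hypotheses fits the first.

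**Step 3: what 16 completers can show on the comparative reading.** Assumptions: a paired t-test, 15 degrees of freedom, units of the SD of the paired difference. The documents give no SD.

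- 95% CI half-width: t(0.975, 15)/√16 = 2.131/4 = 0.533 SD.
- True difference 0.5 SD: noncentrality 0.5 × √16 = 2.0, power 0.465, so it is missed 1 − 0.465 = 0.535, about 54% of the time.
- True difference 0.75 SD: noncentrality 0.75 × √16 = 3.0, power 0.801.

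**Step 4: reference time and deciding time point.** Two references (M1, M2) and two outcomes (M3, M4) give 2 × 2 = 4 candidate contrasts per hypothesis. I simulated null trials with n = 16, two-sided 0.05 for each contrast, counting a false positive if any candidate is significant:

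| Rule | False-positive rate |
|---|---|
| Free choice among four, not gated on an overall test | about 13% to 17% (16% to 17% with equal correlation between time points; 15% falling to 13% with serial correlation 0.3 rising to 0.9) |
| M1 fixed as reference, M3 or M4 free | about 8% to 9% |
| Free choice among four, but only if a condition-by-time multivariate test is significant | about 2% to 3% |

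The last row holds only when there are no true effects anywhere. If tDCS really moves M2 in one condition, the gate tends to open and no longer protects the other contrasts.

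**Step 5: does the plan fix the reference?** Section 7.1 treats tDCS plus rTMS as the intervention, which makes M1 the natural pre-intervention measure. That leans toward M1. It is not conclusive, because M2 lies within the M1 to M3 range cited there. I take M2 as measured after tDCS, as 1.1 states and the order of steps in 12.1 shows, although 12.1 labels it a pre-tDCS measure.

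**The case against.** The strongest reply is that a difference test is not the wrong tool at all. If Hypotheses 2 and 3 mean that inhibition still occurs after anodal or sham priming, a significant within-visit fall supports them. This stands. A reader might infer that no difference test could support these hypotheses, but that is true only of the comparative reading. On the other reading the gap is that no within-visit contrast is named.

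A second reply concerns error rates. A reader might take 13% to 17% as the plan's false-positive rate, or conclude that the reference time is wholly open. The documents support neither. That rate assumes the only named test is bypassed, and 7.1 leans toward M1. Equally, 13.1 does not say that contrasts are gated on the MANOVA or that a condition-by-time test is meant, so 2% to 3% cannot be claimed for the plan either. Taken alone, the missing reference time and M3/M4 rule are missing detail.

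Third, this is a small proof-of-principle trial, the hypotheses are phrased as expectations, and nowhere does it say that non-significance will be reported as proof of no effect. That is correct, and no such intention is attributed here. But a validation study still needs a stated result that counts for or against each prediction.

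Finally, the baseline wording in 2.2 describes earlier work. It helps to interpret the hypotheses but does not define this trial's endpoint.

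**Conclusion.** The point holds in a limited form. Followed as written, the omnibus MANOVA does not isolate the cathodal reversal. A non-significant result would not support Hypotheses 2 and 3 as comparisons, and Hypothesis 3 so read has no comparator in this design. As within-visit predictions they are testable, but the test is not named.

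For size, the firmest figures are the 0.53 SD half-width and the 54% chance of missing a true 0.5 SD anodal-sham difference. Both assume 16 completers and a paired t-test at two-sided 0.05. The false-positive figures run from about 2% to 17% depending on rules that the plan does not state, so they illustrate why those rules matter and do not estimate the plan's error rate.

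The data would remain usable. What is missing is the link from each hypothesis to a result, and it should be written down before unblinding.

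**What to change.** Amend 1.2 and 13.1. The MANOVA may stay as the overall test.

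1. **Hypothesis 1:** test the paired cathodal minus sham difference in MEP change. Report the within-visit cathodal and sham changes from both M1 and M2 before using the word reversal, so that a return to baseline can be told from a rise above it.
2. **Hypothesis 2:** report the within-visit anodal change and the paired anodal minus sham difference, each with a 95% CI. If the difference is not significant, report that a difference was not shown, and do not conclude that there is no effect.
3. **Hypothesis 3:** reword as a within-visit fall in MEP amplitude after rTMS in the sham visit, reported with a 95% CI.
4. **For these contrasts:** before unblinding, state one reference time and one rule for M3 and M4, for example their mean, or both with a Holm adjustment.

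The cost is text only, with no new subjects, visits or data, and no equivalence margin is required. The downsides are that the team must commit to its contrasts early and that Hypothesis 2 may have to be reported as inconclusive.

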2.3. *rTMS is a relatively new therapeutic modality that shows great promise in the treatment and evaluation of a variety of conditions and is already FDA-approved for the treatment of depression. However, various target stimulation parameters and protocols make comparison across research groups difficult, leading to a knowledge gap. Validating a systematic methodological approach in healthy people will allow comparison to previous work as well as establishing a baseline for moving forward to compare metaplasticity in brain disease states.*

3. Study Design

3.1. *This will be a randomized, sham-controlled, double blinded crossover trial in a healthy population.*

[figure not shown]

Figure 1: Subjects will enter the randomization at green diamond. Example shown for a subject following the red line through 3 interventions and another example shown in the blue line receiving a different order of interventions. They will be randomized to a three-visit crossover with a week separation between each visit. There will be four measures taken each visit (M1-M4), which will be approximately 10 minutes apart. Measures taken at each time point include: physiological measures (e.g. MEP), behavioral outcomes (e.g. reaction time) and exploratory outcomes. Study is completed at the end of visit 3 (red octagon). C tDCS=cathodal tDCS; A tDCS=anodal tDCS.

3.2. *Participants will be blinded to treatment group. A team investigator, off-line, will conduct the raw data analysis (e.g. MEP amplitude and CSP) and will be different than the investigator applying the noninvasive neurostimulation to the*

PROTOCOL TITLE: *Metaplasticity in the human motor cortex: validation of an experimental design and comparison of motor outcome measure sensitivity to change*

treatment group. This additional blinding of the data analysis will help to provide another protection against bias.

4. Inclusion and Exclusion Criteria

4.1. Individuals will be screened for eligibility by a study team member. The study team member will ask the potential participant a series of questions to determine whether or not they meet the inclusion/exclusion criteria.

4.2. Inclusion Criteria:

- a) Participant must be at least 18 years of age (all genders, races, and ethnicities)*
- b) Participant must have no current psychiatric or neurologic issues*
- c) Participant must not have any conditions listed in the exclusion criteria*
- d) Participant must be fluent in English*

Exclusion Criteria:

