- 6.1. *Study subjects will participate in three visits total. Each visit will consist of a visit length of 1 to 1 ½ hours in duration. The visits will be approximately one week apart. There will be no scheduled follow-up after the third subject visit. We anticipate that it will take 8 months to enroll all subjects. We expect to complete enrollment of all subjects and completion of experiments in 1 year. We expect data analysis and publication to occur within 2 years of study commencement.*

7. Study Endpoints

- 7.1. *The primary endpoint will be change in motor evoked potential (MEP) amplitude over the first dorsal interosseous (FDI) muscle of the dominant (right) hand pre- and post-intervention (tDCS and rTMS—time points M1-M3) as well as 10 minutes post intervention (time point M4). The secondary endpoint will be the comparison in an exploratory but systematic fashion various measures of motor cortex excitability (e.g. peak-to-peak amplitude change in motor evoked potential (MEP), the integrated area of the MEP (root mean square), the cortical silent period (CSP)), and behavioral measures (reaction time).*
- 7.2. *We will collect data on the safety of rTMS in this patient population including expected side effects: headache (expected 17% with transient headache that responds to simple analgesic) and nonspecific feelings of discomfort. We will collect data on rare but serious adverse events such as seizures (reported at 1.4%). No seizures have been reported in the literature on rTMS in the dystonia population thus far (Lefaucheur et al., 2014).*

8. Research Setting

- 8.1. *The study visits will all take place in the Noninvasive Neurostimulation Lab located on the 2nd floor of the Clinical and Translational Science Center (CTSC).*
- 8.2. *Potential subjects will be recruited and identified through the healthy participant registry through the CTSC as well as fliers placed throughout the Health Sciences Center and Main Campus.*

PROTOCOL TITLE: *Metaplasticity in the human motor cortex: validation of an experimental design and comparison of motor outcome measure sensitivity to change*

8.3. *Research procedures will be performed in the Noninvasive Neurostimulation Lab located on the 2nd floor of the CTSC. Analysis will be performed between the offices of [name], [name], and the CTSC Biostatistics core.*

8.4. *N/A*

8.5. *N/A*

9. Resources Available

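### Exploratory Aim 2: PCA does not measure sensitivity to change, and the linear regression that could is not defined (minor)

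*Combined protocol and SAP*

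**What the plan says.** Section 1.1 states: "Our secondary objective is to evaluate the sensitivity of motor excitability outcome measures response to the noninvasive neurostimulation (e.g. rTMS and tDCS"). Section 1.2 carries this as "Exploratory Aim 2: To evaluate the sensitivity of motor outcome measures to changes in cortical plasticity". Section 7.1 makes it the secondary endpoint ("The secondary endpoint will be the comparison in an exploratory but systematic fashion various measures of motor cortex excitability"), and the protocol title includes "validation of an experimental design and comparison of motor outcome measure sensitivity to change".

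The measures named are MEP peak-to-peak amplitude, MEP area, cortical silent period (CSP) and reaction time. The Figure 1 caption (Section 3.1) and Section 12.1 show physiological and behavioural measures being taken at every time point, M1 to M4, at each of three visits.

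The whole method is one sentence in Section 13.1: "both a linear regression as well as a Principal Components Analysis (PCA) to identify which cortical excitability factors are most sensitive to change", where the change meant is the change caused by the stimulation. Sections 1.2 and 7.1 restate the aim and add no method. For the regression, no outcome, predictor, treatment of repeated measures or standardisation is given. For the PCA, no input matrix, scaling or reading rule is given.

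**The concern.** Sensitivity to an intervention is a signal-to-noise question: how large is a measure's mean response relative to the variability of that response? PCA finds directions of large variance among the variables entered. Two measures of the same MEP will tend to dominate a first component because they move together across people, whether or not stimulation moved either of them.

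The regression does not settle the matter as written, because the sentence permits several models. One of them answers the question; others rank on a different quantity or on the choice of units. The same data could therefore name different measures, depending on choices made after the results are seen. At stake is the answer to the secondary objective, and hence the choice of measure for the patient studies that Section 1.1 gives as the future direction.

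**Working it through.** **Inputs.** From the documents: 16 participants with a ceiling of 20 (Sections 5.2, 5.3, 13.2), three conditions, time points M1-M4 and four named measures. There is no stated figure for Aim 2 to reproduce. Effects, correlations, SDs and test-retest values below are assumptions.

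**Step 1: PCA within one condition (exact).** Let d be a participant's vector of changes, with mean μ. PCA uses the covariance or correlation of d - μ. Replacing d by d + c leaves d - μ unchanged, so the loadings are unchanged for any c. Numerically, shifting the mean change altered loadings by at most 4e-16. In one sample, moving the true CSP response from 0 to 1.5 to 5 SD left the loadings at 0.574, 0.564, 0.368 and 0.465, while CSP's standardised mean change went from 0.15 to 1.82 to 5.71.

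**Step 2: PCA with conditions pooled.** A shift of e SD in one of three conditions adds between-condition variance (2/9)e². Its share of the pooled variance is (2/9)e² / (1 + (2/9)e²): for e = 1.5, 0.5/1.5 = 33%; for e = 3, 2/3 = 67%. So response does enter, but the scaling decides whether it shows. With assumed correlations of 0.9 within the MEP pair, 0.3 between CSP and MEP, and 0.1 for reaction time, covariance PCA put the responsive measure first in 42% of runs (1.5 SD) and 99% (3 SD). Correlation PCA did so in 0%. Those runs used equal variances; in raw units the leading measure also changes with the units.

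**Step 3: regression on within-person change.** Regressing change on an intercept gives t = mean/(SD/√n) = SRM × √n, where SRM is the standardised response mean (mean divided by SD of the paired change). At n = 16, t = 4 × SRM, so with equal n it ranks measures exactly as the SRM does. This form answers the question.

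**Step 4: regression of raw values on time, no participant term.** With a shift δ in between-person SDs and test-retest correlation ρ, SRM = δ/√(2(1-ρ)), but this regression has expected t of about δ√(n/2) = 2.83δ, which ignores ρ. Assume MEP δ = 0.6, ρ = 0.5 and CSP δ = 0.4, ρ = 0.9:

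| | SRM | t on change (4 × SRM) | t, raw on time (2.83δ) |
|---|---|---|---|
| MEP | 0.6/√1.0 = 0.60 | 2.40 | 1.70 |
| CSP | 0.4/√0.2 = 0.89 | 3.58 | 1.13 |

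The order reverses. In simulation the top measure differed in 60-62% of runs. With ρ = 0.7 for all measures the two forms put CSP first about equally often (16-19% and 15-18%), though the top measure still differed in 30-33% of runs.

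**Step 5: raw coefficients.** Assume SRMs of 1.0, 0.8, 0.3, 0 for amplitude, area, CSP and reaction time, and change SDs of 0.5 mV, 0.1 mV, 20 ms, 30 ms. The mean changes are 0.5 mV, 0.08 mV, 6 ms and 0 ms. In mV, amplitude (0.5) is below CSP (6); in microvolts it is 500 and far above. The ranking follows the unit.

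**Step 6: a selection rule, for illustration.** The rule is the largest first-component loading in single-condition correlation PCA, n = 16, with MEP-pair correlation 0.5-0.9 and other correlations 0.1-0.2:

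| True SRM (amplitude, area, CSP, reaction time) | MEP measure leads the first component | SRM names the right measure |
|---|---|---|
| 0.3, 0.3, 1.0, 0 | 79-99.9% | CSP, 93-95% |
| 1.0, 0.8, 0.3, 0 | 78-100% | an MEP measure, 96-98% |
| 0, 0, 0, 0 | 78-100% | not applicable |

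The loading rule does not track response. Two of the four measures are MEP, so chance is already 50%; with all correlations set to 0.5, each measure led about 25% of the time in every pattern. The last column is partly built in, because the best measure was defined by its SRM.

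**The case against.** The strongest reply is that the plan never says PCA will be run on change scores within one condition, and never says the largest loading selects the measure. Both are assumptions made here. The trial is a three-condition crossover, and pooled covariance PCA partly reflects response (Step 2). The word factors may also mean components that are then tested for change. That stands, so a reader should not infer that PCA always ignores the response, or that Aim 2 cannot be answered with the methods named. The component reading is still weak under the Step 6 assumptions: the component with the largest mean-score t was CSP-led in 46-59% of runs when CSP was best, and MEP-led in 69-77% when MEP was best.

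A second reply is that the percentages reproduce their inputs. That stands too. They show that permitted readings can disagree, not how often this trial would name the wrong measure. Nothing in the protocol says raw coefficients would be ranked across units.

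A third is that an exploratory aim need not be fully specified. This limits the severity. It does not remove the mismatch between tool and question, and the plan itself promises a systematic comparison.

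**Conclusion.** The point holds as a minor one. PCA does not measure sensitivity to change, and the regression that could is left undefined. Three results need no assumed values: within-condition loadings are invariant to the mean response, t on within-person change equals SRM × √n, and Section 13.1 contains no model specification. Every simulated percentage rests on assumed correlations, effects and test-retest values.

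A reader might infer that the planned analysis will pick the wrong measure, or that the trial's main result is compromised. The documents support neither. A standardised regression on within-person change falls within the current sentence and would answer the question, and Aim 1 and its sample size do not depend on Aim 2.

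**What to change.** Before analysis, replace PCA as the selection tool in Section 13.1 with text along these lines:

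- For each measure (MEP amplitude, MEP area, CSP, reaction time), estimate the standardised within-person response: mean divided by SD of the paired change, or the equivalent standardised coefficient from a within-participant model with a period term for the three visits.
- Name one leading contrast, for example the M1-to-M3 change, cathodal minus sham. One is needed: in simulation, cathodal-minus-sham and sham-only M1-to-M3 indices named different top measures in 4-41% of runs, depending on how far the measures differed.
- Add supportive contrasts for tDCS alone (M1-to-M2, each active condition minus sham) and rTMS alone (M2-to-M3 in the sham session), because the secondary objective names both. Section 12.1 lists rTMS at every visit and no sham rTMS, so the last contrast cannot be separated from drift.
- Report differences in absolute SRM between measures, with intervals from resampling participants together with all their sessions. Declare no winner.
- Use PCA on the correlation matrix only to describe redundancy among measures.

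Downsides to state (simulated without a period term):

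- Intervals are wide. At n = 16, true SRMs of 1.0 and 0.3 give a half-width of about 0.8 and are separated in about 45% of runs; 0.6 and 0.3 in 10-11%. At 20 participants these become 56% and 14%.
- Absolute SRM is biased upward: a measure with no true change averages 0.21 at n = 16.
- The percentile bootstrap 95% interval is somewhat anti-conservative, with about 5-9% false separation against 5%, so it should be labelled approximate.

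The SRM is one valid index among several; what matters is fixing one in advance. The cost is wording and a few lines of code on measures already collected, with no change to visits or sample size.

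A separate clerical point: Section 12.1 labels M2 with "pre-tDCS measurement): neurophysiological outcome assessment (MEP, CSP) and behavioral outcome (reaction time task"), although it is listed after tDCS, while Section 1.1 has "directly after priming tDCS [M2], directly after inhibitory rTMS [M3], and 10 minutes after inhibitory rTMS [M4"]. The two should be reconciled so that the M1-to-M2 contrast is unambiguous.
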